## STUDY PROTOCOL

This study was a randomized controlled trial of healthy participants. After providing written informed consent, participants were screened for eligibility criteria. Eligible participants then underwent Quantitative Sensory Testing procedures that included Heat Pain Threshold (HPT), Temporal Summation (TS), Pressure Pain Threshold (PPT), and Conditioned Pain Modulation (CPM).

During HPT, participants were provided a thermode attached to a TCS-II (QST.Lab, Strasbourg, France). The thermode increased from a baseline of 32 degrees Celsius at 1 degree C/second to a maximum of 50 degrees Celsius. Participants were instructed to indicate when the sensation first changed from warmth to pain (pain threshold) by pressing a button. Once the button was pressed, the temperature stopped increasing and quickly returned to a baseline temperature of 32 degrees Celsius. Two trials were completed at the dominant quadriceps and ipsilateral upper trapezius.

During TS, participants placed the thermode on the palmar surface of the hand. Participants rated the pain intensity during a train of 10 heat pulses that were delivered to the skin with temperatures peaking at 49°C at a rate to maintain the desired inter-stimulus interval.

For PPT, a computerized pressure algometer (AlgoMed, Ramat Yishai, Israel) with a 1 cm diameter rubber tip was applied at a constant rate. Participants were instructed to press a response button connected to the algometer when the sensation first changed from pressure to pain (pain threshold). Two trials were performed at the dominant quadriceps and ipsilateral upper trapezius.

For CPM, PPT was applied to the web space of the non-dominant foot. Participants then immersed the dominant hand into water cooled by a refrigeration unit (ARCTIC Series Refrigerated Bath Circulator, ThermoFisher Scientific, Massachusetts, USA) that circulated water continuously to maintain a constant temperature of 12° Celsius for 60 seconds. PPT measurement was then repeated.

After Quantitative Sensory Testing, participants completed a 1-repetition maximum test for a leg extension exercise with the dominant lower extremity.

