Participants were then randomly assigned to either the high intensity exercise, low intensity exercise, or quiet rest intervention. For participants assigned to the exercise interventions, individuals completed a single leg knee extension exercise for 3 sets, 10 repetitions on the dominant leg. A weight corresponding to either 30% or 75% of the participants 1-repetition maximum was added for the low intensity or high intensity group, respectively. For individuals assigned to the quiet rest intervention, participants sat quietly for two minutes three sets. Between each set or exercise or quiet rest, PPT was measured on the dominant quadriceps and upper trapezius.

After exercise, CPM was repeated.

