## STATISTICAL ANALYSIS

To examine the immediate changes in PPT by group, a mixed model ANOVA was conducted. Simple effects decomposition with Bonferroni correction were completed. Our a priori alpha level is <0.05.

A Pearson correlation examined for the association of HPT, TS, baseline PPT with Exercise-Induced Hypoalgesia.

To examine if CPM efficiency changes by group, a mixed model ANOVA was conducted.

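### The Pearson correlations with Exercise-Induced Hypoalgesia include no comparison with quiet rest, so they cannot show that an association is specific to exercise

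*Combined protocol and SAP*

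**What the plan says.** The protocol section sets out three randomised arms: "Participants were then randomly assigned to either the high intensity exercise, low intensity exercise, or quiet rest intervention". The candidate measures are taken before randomisation: "Eligible participants then underwent Quantitative Sensory Testing procedures that included Heat Pain Threshold (HPT), Temporal Summation (TS), Pressure Pain Threshold (PPT), and Conditioned Pain Modulation". PPT is then followed in all arms, including the control: "Between each set or exercise or quiet rest, PPT was measured on the dominant quadriceps and upper trapezius".

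The statistical section covers the association question in one sentence: "A Pearson correlation examined for the association of HPT, TS, baseline PPT with Exercise-Induced Hypoalgesia". It does not define Exercise-Induced Hypoalgesia as a variable, say which arms or PPT sites enter, or mention stratification, an arm term or an interaction.

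Arm does appear in the other two analyses: "To examine the immediate changes in PPT by group, a mixed model ANOVA was conducted", and "To examine if CPM efficiency changes by group, a mixed model ANOVA was conducted". The significance level is given as "Our a priori alpha level is <0.05"; sidedness is not stated.

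**The concern.** The outcome is named as something that exercise induces. Finding that a sensory measure is associated with it, and not merely with PPT changing over a session, requires comparing the association under exercise with the association at rest. The quiet-rest arm supplies that comparison and its PPT data are collected, but a two-variable correlation has no place for it.

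Two errors are then possible. An association that is equally present in people who only sat quietly could be read as one with response to exercise. Conversely, if all arms are pooled, a real exercise-specific association is diluted by rest participants. Baseline PPT is the most exposed of the three measures, because it may also be part of the outcome.

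**Working it through.** The documents give no sample size, allocation ratio, SD or expected correlation, so there is no stated figure to reproduce. Everything below is illustrative: three equal arms, two-sided alpha 0.05, and the sizes shown.

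**Step 1. The three possible readings.**
- Pooled over arms: resting change is counted as exercise-induced, and rest is not used as a comparator.
- Exercise arms only: rest is left out of this question, so drift, habituation or regression to the mean is credited to exercise.
- Within each arm: the numbers can be set side by side, but no test compares them. Significant in one arm and non-significant in another is not a test of difference.

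**Step 2. Same association in every arm, nothing specific to exercise.** Simulated at 20 per arm (4,000 replicates; assumed arm mean shifts 0.5, 0.3 and 0 SD). The table gives the share of trials with p < 0.05:

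| True r in every arm | Pearson, exercise arms | Pearson, pooled | Predictor x (exercise vs rest) |
|---|---|---|---|
| 0.2 | 25% | 35% | 5% |
| 0.3 | 48% | 64% | 4% |
| 0.4 | 75% | 89% | 5% |

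The pooled column depends somewhat on the assumed arm shifts; another run gave 30%, 60% and 86%.

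**Step 3. Can the exercise-arms correlation tell the two situations apart?** With a slope of 0.4 residual SD at 20 per arm (3,000 replicates), the exercise-arms correlation has mean r 0.36 and is significant in about 65% of trials when the slope is shared by all arms. It has mean r 0.36 and is significant in about 66% when the slope exists only under exercise. It does not distinguish them.

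**Step 4. Baseline PPT.** Assume the outcome is post minus pre, with equal variance s² and pre-post correlation r. Then cov(pre, post - pre) = (r - 1)s² and var(post - pre) = 2(1 - r)s², so

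corr(pre, change) = -(1 - r)/sqrt(2(1 - r)) = -sqrt((1 - r)/2).

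| r | Expected correlation | Pooled Pearson significant, 20 per arm | Interaction significant |
|---|---|---|---|
| 0.7 | -sqrt(0.15) = -0.39 | 87% | 5% |
| 0.8 | -sqrt(0.10) = -0.32 | 68% | 6% |
| 0.9 | -sqrt(0.05) = -0.22 | 36% | 5% |

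The closed form applies within an arm, resting arm included. The simulated columns used 3,000 replicates and modest arm mean shifts. Subtracting baseline lowers the baseline slope by exactly 1 in every arm, so the difference in slopes between exercise and rest is unaffected by the coupling.

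**Step 5. Association only under exercise (r about 0.42), 20 per arm.** The exercise-arms Pearson has about 78% power. Pooling lowers r to about 0.28 and power to about 60%. The interaction test has about 35% power at 20 per arm, 51% at 30 and 63% at 40.

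**The case against.** Several points on the other side stand.

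- **Silence is not a decision.** A reader might infer that the plan deliberately pools the arms or ignores them. The text does not say so; within-arm correlations are compatible with it and would allow a descriptive look at exercise against rest. What is certain is that the contributing arms are unstated and no comparison is planned.
- **Quiet rest is used.** A reader might infer that the control arm is wasted. It is a group in both mixed model ANOVAs, so that holds at most for the correlation.
- **The plan speaks of association.** It makes no claim of prediction or moderation, and does not call this analysis primary or confirmatory. If a descriptive association is all that is intended, Pearson is not a calculation error.
- **The percentages are not false-positive rates of the correlation.** In step 2 an association with PPT change really exists. Detecting it is an error only if it is then described as exercise-specific.
- **The remedy is costly in power.** At 20 per arm it has about 35% power against 78% for the exercise-arms correlation, below even the pooled 60%. That is a serious loss, although the 78% is power to detect any association in those arms, not an exercise-specific one.

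These points narrow the concern without removing it. On none of the three readings does a planned test address whether the association belongs to exercise.

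**Conclusion.** The concern holds, limited to the correlation analysis. As written, it can describe association with PPT change but cannot support a statement that HPT, TS or baseline PPT relates specifically to hypoalgesia from exercise. The randomised group comparisons are untouched.

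The size rests on assumptions that the documents neither confirm nor contradict: 20 per arm, equal allocation, and the correlations tabulated. The result that does not depend on sample size is qualitative: the exercise-arms correlation looks the same whether or not rest shows the same slope. The baseline PPT result further assumes that the outcome is a change from that same baseline with equal pre and post variance. This should be corrected, because a better analysis is available from data already collected.

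**What to change.** 1. Define Exercise-Induced Hypoalgesia as a variable, including which PPT reading counts as final, and state the sites and contributing arms.
2. For each PPT site, fit final PPT on baseline PPT, arm, the predictor, and predictor x (exercise vs rest). When baseline PPT is itself the predictor, use baseline PPT x (exercise vs rest).
3. Report the slope with its 95% CI in each arm, and label the analysis exploratory.
4. Describe an association as exercise-specific only if the interaction supports it. Otherwise report the correlations as descriptive associations with PPT change.
5. State that a non-significant interaction is not evidence of no effect, given the low power shown above.

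The cost is a change of wording and one regression per predictor and site. No new data are needed, and it can be run as a reanalysis if data collection is complete. The real price is power.

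### Neither mixed model ANOVA names a baseline covariate, although PPT and CPM are both measured before randomisation: a possible loss of precision, not of validity

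*Combined protocol and SAP*

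**What the plan says.** The Statistical Analysis section has one sentence for each model. For PPT: "To examine the immediate changes in PPT by group, a mixed model ANOVA was conducted". For CPM: "To examine if CPM efficiency changes by group, a mixed model ANOVA was conducted". The follow-up to the PPT model is "Simple effects decomposition with Bonferroni correction were completed". No covariate, time level or interaction term is named for either model. Baseline PPT appears by name only in a separate analysis: "A Pearson correlation examined for the association of HPT, TS, baseline PPT with Exercise-Induced Hypoalgesia".

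The Study Protocol section fixes the order of events. PPT (dominant quadriceps and ipsilateral upper trapezius) and CPM belong to the initial sensory testing. The next step is "After Quantitative Sensory Testing, participants completed a 1-repetition maximum test for a leg extension exercise with the dominant lower extremity", and after that, "Participants were then randomly assigned to either the high intensity exercise, low intensity exercise, or quiet rest intervention". PPT is then measured again between sets at the quadriceps and upper trapezius, and CPM is repeated once after the intervention.

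**The concern.** Both baselines precede randomisation, so adjusting for them is safe and needs no new data. A test of change fixes the weight on baseline at 1, whereas a baseline-adjusted comparison estimates that weight. When the best weight is below 1, the change score carries baseline noise that adjustment would remove. With the same participants, a real difference between an exercise intensity and rest could then be somewhat more likely to be missed. What is at stake is the width of the intervals and power.

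**Working it through.** The document states no sample size, SD, correlation, effect size or power, so there is no planned figure to reproduce. The design facts below come from the Study Protocol section. Every value of rho, SD ratio and slope is assumed.

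**1. What the planned CPM test is.** There is one CPM assessment before and one after the intervention, in three arms. With two time points, the group-by-time F is the one-way F on post minus pre. If the CPM score is a simple difference in PPT, entering the raw PPT readings and testing group x time x conditioning gives the same test. In one simulated data set (20 per arm), all three routes gave F = 14.2043 on 2 and 57 df.

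**2. Precision with a common slope and variance.** Set the pre SD to 1 and the post SD to L, with correlation rho. For weight b on baseline:

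- Var(post - b x pre) = L² + b² - 2b·rho·L
- Change score, b = 1: 1 + L² - 2·rho·L
- Adjusted, b = rho·L: L²(1 - rho²)
- Difference between the two: (1 - rho·L)²

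The difference is never negative and is zero only when rho·L = 1. The variance ratio, adjusted to change, is L²(1 - rho²) / (1 + L² - 2·rho·L). At L = 1 this reduces to (1 + rho)/2.

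| rho | L = 1 | L = 1.25 |
|---|---|---|
| 0.5 | 0.75/1.00 = 0.75 | 1.1719/1.3125 = 0.89 |
| 0.7 | 0.51/0.60 = 0.85 | 0.7969/0.8125 = 0.98 |
| 0.8 | 0.36/0.40 = 0.90 | 0.5625/0.5625 = 1.00 |
| 0.9 | 0.19/0.20 = 0.95 | 0.2969/0.3125 = 0.95 |

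At equal SDs, the extra sample needed by the change score for the same precision is 1/0.75 - 1 = 33% at rho 0.5 and 1/0.95 - 1 = 5% at rho 0.9.

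**3. Small arms.** Estimating the slope uses up part of the gain. In simulation (three arms, equal SDs, rho 0.8), the ratio was 0.96 at 10 per arm, 0.93 at 20 and 0.92 at 30, against 0.90 in theory.

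**4. PPT.** For the average of k post-baseline readings under compound symmetry, with v = (1 + (k - 1)rho)/k, the ratio is (v - rho²)/(v + 1 - 2·rho). Three sets give two between-set readings; the protocol does not say whether another follows the last set. For k = 2 the ratio is 0.50/0.75 = 0.67 at rho 0.5 and 0.14/0.15 = 0.93 at rho 0.9. For k = 3 it is 0.63 and 0.93 (0.625 and 0.925). These figures add the assumptions of equal SDs and compound symmetry.

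**5. When slopes differ by arm.** Assume slopes of 1 (rest), 1 (low) and 0.4 (high), pre SD 1, residual SD 0.5 and equal arms. The pooled slope is (1 + 1 + 0.4)/3 = 0.8. The per-participant variance in an arm is (arm slope - b)² + 0.25.

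- Low vs rest: change 0.25 + 0.25 = 0.50; pooled adjustment 0.29 + 0.29 = 0.58; ratio 1.16.
- High vs rest: change 0.61 + 0.25 = 0.86; pooled adjustment 0.41 + 0.29 = 0.70; ratio 0.81.

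Simulation agreed: 1.14 and 0.82 at 100 per arm. Adjustment with one pooled slope can therefore lose precision for one pairwise contrast while gaining it for another.

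**The case against.** The best defence is that the planned ANOVA is a valid analysis of a randomised comparison, and that the plan asks about changes, which a baseline-as-time-level model addresses directly. This stands. A reader might infer from the missing covariate that baseline is ignored or that the results are biased. The document does not support either: the wording about change suggests that baseline is in the model, and randomisation after baseline makes this a matter of efficiency.

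A second objection is that adjustment is not uniformly better. This also stands. A reader might infer that a baseline-adjusted comparison can never be less precise, but that needs similar slopes and variances across arms. Three different interventions could break this condition, and Bonferroni-corrected simple effects may report exactly the pairwise contrasts where it matters. In the unequal-slope example the omnibus test still favoured adjustment.

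Third, the model itself is inferred, because neither the time levels nor the CPM score is defined. That is why the fix begins with stating the terms. Had post-intervention values alone been analysed, the equal-SD comparison would be 1 - rho² (0.75 at rho 0.5, 0.36 at 0.8), a larger loss, but the wording about change makes this reading less likely.

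Finally, the section is written in the past tense. Choosing a covariate after seeing results adds analyst discretion, which limits what can be recommended but does not remove the point.

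**Conclusion.** The point holds as a modest one about efficiency. Two baselines measured before randomisation are not named as covariates, and on the likely reading the CPM analysis is a change-score comparison. With similar slopes and variances across arms, that comparison is asymptotically no more precise than an adjusted one, and less precise unless rho x (post SD / pre SD) = 1. For one pre and one post value, the adjusted-to-change variance ratio is 0.75 to 0.95 over rho 0.5 to 0.9 with equal SDs, and 0.89 to 1.00 with the post SD 1.25 times the pre SD. With unequal slopes, a single contrast can go the other way, as with 1.16 in the example.

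The actual loss cannot be known from the document and may be nil at high correlation, in very small arms, or with a larger post-intervention SD. A reader might infer a definite loss of power, or that the trial was underpowered; with no sample size, SD or correlation stated, neither can be claimed. The point is worth considering and does not call the planned analysis into question.

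**What to change.** 1. State the time levels, the model terms and the test of interest for both ANOVAs, and define the CPM score.
2. For CPM, compare post-intervention CPM between groups with pre-intervention CPM as covariate.
3. For PPT, use one of two models for the between-group comparisons. The first adjusts post-baseline PPT for baseline PPT at the same site, and tests the group effect as well as group-by-time. An effect that is constant across post-baseline readings sits in the group term, and the group-by-time test alone would detect it only at the 5% error rate. The second keeps baseline as a time level with baseline means constrained equal across arms, which randomisation after baseline justifies.
4. Check the group-by-baseline interaction. If slopes differ, use arm-specific slopes with baseline centred. In the example above this brings the low-vs-rest ratio back to 0.50/0.50 = 1.00 in large samples.
5. Keep the Bonferroni correction. Take within-group changes from the planned ANOVA or the constrained model, since a model of post-baseline values alone cannot give them.
6. If results have already been seen, report the adjusted analyses as labelled sensitivity analyses beside the planned ANOVA.

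The cost is one degree of freedom per covariate (three instead of one with arm-specific slopes) and some re-analysis. No new data are needed.
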